9.7.1.8.3 LABORATORY VALUES

Laboratory results will be summarized using Système International units, as appropriate. For all quantitative parameters listed in [Section 9.5.1.5.3](#), the actual value and the change from

baseline to each postbaseline visit and to the end of treatment (defined as the last on-treatment value) will be summarized by visit and treatment group using descriptive statistics. Percentages will be based on the number of subjects with both nonmissing baseline and relevant postbaseline results.

Laboratory test results will be assigned a low/normal/high (LNH) classification according to whether the value was below (L), within (N), or above (H) the laboratory parameter's reference range. Within-treatment comparisons for each laboratory parameter will be based on 3-by-3 tables (shift tables) that compare the baseline LNH classification to the LNH classification at the End of Treatment and the Follow-Up visits. Similar shift tables will also compare the baseline LNH classification to the LNH classification for the highest and lowest value during the treatment period.

[Appendix 1](#) presents the criteria that will be used to identify subjects with treatment-emergent markedly abnormal laboratory values (TEMAV). Except for phosphate, a TEMAV is defined as a postbaseline value with an increase from baseline to a grade of 2 or higher. For phosphate, a TEMAV was defined as a postbaseline value with an increase from baseline to a grade of 3 or higher. When displaying the incidence of TEMAVs, each subject may be counted once in the laboratory parameter high and in the laboratory parameter low categories, as applicable.

9.7.1.8.4 VITAL SIGNS

Descriptive statistics for vital signs parameters (eg, systolic and diastolic BP, pulse, respiratory rate, temperature, weight) and changes from baseline will be presented by visit and treatment group.

9.7.1.8.5 ELECTROCARDIOGRAMS

For each ECG parameter (including PR interval, RR interval, QRS interval, QT interval, QTc interval (Bazett formula), QTc interval (Fridericia formula), and heart rate), the actual value and change from baseline will be summarized by visit and treatment group using descriptive statistics.

Shift tables will present changes from baseline in ECG interpretation (categorized as normal; abnormal, not clinically significant; and abnormal, clinically significant) to end of treatment.

Maximum postbaseline QTc (Bazett) and QTc (Fridericia) will also be tabulated by treatment group as follows:

- Number (percentage) of subjects in greater than 450 msec, greater than 480 msec, and greater than 500 msec during the treatment, and
- Number (percentage) of subjects with an increment of greater than 30 msec and greater than 60 msec from the baseline visit.

9.7.1.8.6 OTHER SAFETY ANALYSES

Other safety assessments including adolescent growth evaluations using 95th percentile CDC growth charts and bone age using x-ray of the hand, sexual maturation as measured in Tanner Staging, study drug effect on cognition assessed by Leiter-3, assessment of suicidality using C-SSRS, and depression assessment using PHQ-9 will be summarized by treatment group at each scheduled visit. For echocardiographic assessments, the proportion of subjects who develop FDA-defined valvulopathy, the proportion of subjects who develop pulmonary hypertension (defined as when a subject's SPAP is ≥ 40 mmHg evaluated by echocardiograph], and change from baseline in SPAP will also be summarized by treatment group at Week 28 and Week 52. (revised per Amendment 01)

9.7.2 Determination of Sample Size

The proposed sample size is based on the comparison of the primary efficacy endpoint, change from Baseline in BMI at Week 52 between the Belviq XR 20-mg treatment group and placebo group. Assuming a SD of 2.2 kg/m² and a 40% dropout rate, a sample size of 260 subjects in a 1:1 ratio (n=130 in the Belviq XR 20-mg treatment group; n=130 in the placebo group) will have at least 80% power to detect a treatment difference of 1 kg/m² in BMI, using a 2-sided t-test with $\alpha=0.05$. Assuming the proportion of subjects achieving at least a 5% BMI reduction at Week 52 is 20% for the placebo group and a 40% dropout rate, this sample of 260 subjects (130 subjects for Belviq XR 20 mg and 130 subjects for placebo) will also have greater than 78% power to detect an absolute difference of 20% between the Belviq XR 20-mg group and placebo group, using a 2-sided Chi-Square test with $\alpha=0.05$. The assumption used in the sample size calculation is based on the 2 pivotal lorcaserin studies, APD356-009 and APD356-011 in obese and overweight non-diabetic adult subjects. (revised per Amendment 02)

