The proposed sample size is based on the comparison of the primary efficacy endpoint, change in BMI from Baseline to Week 52 between the Belviq XR 20-mg treatment group and placebo group. Assuming a SD of 2.2 kg/m^2 and a 40% dropout rate, a sample size of 260 subjects in a 1:1 ratio ($n=130$ in the Belviq XR 20-mg treatment group; $n=130$ in the placebo group) will have at least 80% power to detect a treatment difference of 1 kg/m^2 in BMI, using a 2-sided t-test with $\alpha=0.05$. Assuming the proportion of subjects achieving at least a 5% BMI reduction at Week 52 is 20% for the placebo group and a 40% dropout rate, this sample of 260 subjects (130 subjects for Belviq XR 20 mg and 130 subjects for placebo) will also have greater than 78% power to detect an absolute difference of 20% between the Belviq XR 20-mg group and the placebo group, using a 2-sided Chi-Square test with $\alpha=0.05$. The assumption used in the sample size calculation is based on the 2 pivotal lorcaserin studies APD356-009 and APD356-011 in obese and overweight non-diabetic adult subjects. (revised per Amendment 02)

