9.7.1.2 Definitions of Analysis Sets

- The Safety Analysis Set is the group of subjects who received at least 1 dose of study drug and had at least 1 postdose safety assessment.
- The Full Analysis Set (FAS) is the group of all randomized subjects regardless of adherence to study drug.
- Per-Protocol Analysis Set (PP) is the group of all randomized subjects who are 80% or greater compliant with study medication, completed the study, have no major protocol deviations, have no violations of inclusion or exclusion criteria, and have BMI data at Baseline and Week 52. The determination of subjects to be excluded from this population based on the above criteria and list of major protocol violations will be included in the SAP and finalized before data base lock.
- The PD Analysis Set is the group of subjects who had sufficient PD data to derive at least 1 PD parameter.
- The PK Analysis Set is the group of all randomized subjects from whom at least 1 valid lorcaserin plasma concentration was obtained with associated documented dosing history.
- The population PK/PD set is the group of randomized subjects with PK information and who have at least 1 adequately documented measurement of BMI.

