9.7.1.6 Efficacy Analyses

The FAS will be used as the primary analysis set for all efficacy analyses, while the PP will be used as a supportive analysis. Unless specified otherwise, a 2-sided $\alpha=0.05$ significance level will be used for all efficacy analyses.

Primary Efficacy Analysis

The primary efficacy endpoint is the change in BMI from Baseline to Week 52. The change from baseline in BMI will be analyzed using analysis of covariance model (ANCOVA) with factors of treatment, sex (male and female) as fixed effect, and the baseline age and BMI as covariates. The missing values will be imputed using a pattern mixture model utilizing multiple imputation (MI) assuming the missing values are missing not at random (MNAR). The missing values will be imputed at each visit using all available values including the retrieved measurement from the postdiscontinuation data. The details of the analysis model and missing value imputation method will be further described in the SAP.

In addition, the following analyses will also be considered as sensitivity analyses:

- PP analysis: The same primary efficacy analyses described above will be repeated based on the PP.
- Change from baseline in standardized BMI score (Z-score): The same primary efficacy analyses described above will be repeated using Z-score.

Subgroup analyses and additional sensitivity analyses, if appropriate, may also be performed and will be described in the SAP.

Key Secondary Efficacy Analysis

The key secondary efficacy endpoint is the proportion of subjects achieving at least a 5% BMI reduction at Week 52. The secondary efficacy endpoint will be analyzed only if the test for the primary efficacy endpoint is statistically significant.

The proportion of subjects achieving at least a 5% BMI reduction at Week 52 will be analyzed using a logistic regression model with factors of treatment, and sex (male and female), and baseline BMI as a covariate using FAS. Subjects with any missing assessment at Week 52 will be considered as treatment failures in this analysis.

Other Secondary Efficacy Analyses

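### The power of more than 78% stated for the key secondary responder endpoint is that of a completers-only test, not of the planned analysis with missing values counted as failures

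*Protocol*

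**What the plan says.** The text at issue is the protocol as revised by Amendment 02 (version 7.0).

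- **Power statement, Section 9.7.2.** The placebo responder rate "is 20% for the placebo group and a 40% dropout rate" is assumed. With 260 subjects, 130 per arm, the study "will also have greater than 78% power to detect an absolute difference of 20% between the Belviq XR 20-mg group and placebo group", by a two-sided chi-square test at the 0.05 level. The Sample Size Rationale in the synopsis repeats the statement: "will also have greater than 78% power to detect an absolute difference of 20" points.
- **Planned analysis, Section 9.7.1.6, Key Secondary Efficacy Analysis.** Logistic regression with treatment, sex and baseline BMI, in the Full Analysis Set. On missing data: "Subjects with any missing assessment at Week 52 will be considered as treatment failures in this analysis".
- **Analysis set, Section 9.7.1.2.** "The Full Analysis Set (FAS) is the group of all randomized subjects regardless of adherence to study drug".
- **Follow-up, Sections 9.3.3 and 9.5.5.** Subjects who stop treatment early are to be followed to the end of the study. Investigators are asked to bring early discontinuers back for the primary endpoint measurement.

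**The concern.** The two sections treat the same dropouts differently. The power calculation takes them out of the denominator and leaves the responder rates at 20% and 40%. The analysis keeps them in the denominator as non-responders. That restores the sample size to 130 per arm but dilutes both rates, and with them the difference. The first rule costs sample size only; the second costs effect size.

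The endpoint is the only key secondary one and is tested only if the primary succeeds. A reader who uses the stated power to judge the chance of that second claim is relying on a test that the protocol does not plan to run. Every ingredient (rates, dropout, test, analysis set, failure rule) is fixed in the protocol, so this is not a detail left for the SAP.

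**Working it through.** **Inputs.** Two-sided alpha 0.05; 130 per arm; placebo 20%, active 20% + 20 points = 40%; dropout 40%, one figure for both arms (all Section 9.7.2). Missing at Week 52 counts as failure, in all randomised subjects (Sections 9.7.1.6 and 9.7.1.2).

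**Formula.** Two-proportion test with pooled variance under the null, where p̄ is the mean of p1 and p2:

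Power = Φ{ [ |p2 − p1| − 1.96·√(2p̄(1 − p̄)/n) ] / √[ (p1(1 − p1) + p2(1 − p2))/n ] }

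**Step 1: reproduce the stated figure.** Delete the dropouts: n = 130 × 0.60 = 78 per arm, 0.20 against 0.40, p̄ = 0.30.
- Null SE = √(0.42/78) = 0.0734; alternative SE = √(0.40/78) = 0.0716.
- (0.20 − 1.96 × 0.0734)/0.0716 = 0.784, so power is **78.4%** (78.9% by exact enumeration).

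This matches the protocol's figure.

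**Step 2: apply the planned failure rule to the same inputs.** Take 20% and 40% as rates among subjects with Week 52 data, with 40% missing in each arm. The rates among all randomised are 0.20 × 0.60 = 0.12 and 0.40 × 0.60 = 0.24, n = 130, p̄ = 0.18.
- Null SE = √(0.2952/130) = 0.04765; alternative SE = √(0.288/130) = 0.04707.
- (0.12 − 1.96 × 0.04765)/0.04707 = 0.565, so power is **71.4%**.

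Other versions of the unadjusted test give 71.9% (exact chi-square), 72.2% (unpooled variance), 69.7% (Wald test on the log odds ratio) and 66.7% (Fisher's exact or continuity-corrected).

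**Step 3: the other denominator.** If 20% and 40% are already rates among all randomised, with dropouts counted as failures, n stays at 130 and the rates stay as stated.
- (0.20 − 1.96 × √(0.42/130))/√(0.40/130) = 1.597, so power is **94.5%**.

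**Step 4: fewer missing values.** Rates of 0.20 and 0.40 among observed subjects, failure rule, 130 per arm:

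| Missing at Week 52, each arm | Rates compared | Power |
|---|---|---|
| 40% | 12% v 24% | 71.4% |
| 32% | 13.6% v 27.2% | 78.0% |
| 30% | 14% v 28% | 79.5% |
| 20% | 16% v 32% | 86.0% |
| 10% | 18% v 36% | 90.9% |

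**Step 5: the primary endpoint.** A difference of 1 kg/m², SD 2.2 kg/m² and 78 per arm give 81.0%, in line with the stated minimum of 80%. That statement is not in question here.

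**The case against.** Four objections carry weight.

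- **The 71% is conditional.** The protocol never says whether 20% and 40% are rates among completers or among all randomised. Section 7.1.2 builds the 20-point difference on the 24-point adult result (47% against 23%) without saying how dropouts were counted there. This stands, and it is why the result is a range. Without deleting dropouts, however, the power at 20% against 40% would be 94.5%; the protocol's own calculation therefore uses the rates as completer rates.
- **Dropout need not mean a missing Week 52 BMI.** Subjects who stop treatment are followed, and home visits are an option. This also stands: at about 32% missing or less, power under the failure rule reaches 78%. But Section 9.7.2 itself treats the 40% as unavailable when it reduces n.
- **On the all-randomised reading, 94.5% does exceed 78%.** True. The statement would then be conservative, though the 40% deduction would have no place in it.
- **The planned test is covariate-adjusted.** Adjustment for sex and baseline BMI may move the power somewhat. It does not take the failures out of the denominator.

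Three stronger readings might be inferred and are not supported. First, a reader might conclude that the trial is too small. Section 9.7.2 bases the sample size on the primary endpoint, and that power reproduces. Second, a reader might set the 24% active-arm rate against the 35% criterion in Section 7.1.2. That criterion comes from adult draft guidance, concerns body weight, is one of two alternatives and is not a success criterion of this trial; the section says that no adolescent guidance exists. Third, the failure rule might be read as failing a BMI responder who missed, say, the Week 52 ECG. The sentence directly follows the definition of the BMI responder analysis, so missing BMI is the natural meaning; clearer wording would be an editorial matter.

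**Conclusion.** Wrong as written; should-fix. The arithmetic behind the stated figure is sound for a comparison of completers, but the protocol plans a different analysis. On the protocol's own inputs, with 20% and 40% as rates among subjects with Week 52 data and 40% missing equally in both arms, power is about 71%, some 7 points below the stated figure (78.4 − 71.4 = 7.0). If the rates already refer to all randomised subjects it is about 94%. The first reading follows how the protocol uses its inputs, but the text does not settle the matter, so 71% should not be quoted without its conditions. The test, the significance level and the validity of the analysis are unaffected.

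**What to change.** In the synopsis (Sample Size Rationale) and Section 9.7.2, state which denominator the 20% and 40% refer to, and quote the power of the Full Analysis Set analysis with missing values counted as failures:

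- if they are rates among subjects with Week 52 data: expected rates of 12% and 24% in 130 per arm with 40% missing, power about 71%, preferably with the values for 30%, 20% and 10% missing; or
- if they are rates among all randomised subjects: no dropout deduction, power about 94%.

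The cost is one sentence in each of two places and, on the first reading, a less favourable figure. No change to sample size, test or conduct is needed.

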9.7.3 Interim Analysis

No interim analysis is planned for this study.

9.7.4 Other Statistical/Analytical Issues

Further statistical and analytical issues will be discussed in the SAP.

9.7.5 Procedure for Revising the Statistical Analysis Plan

If the SAP needs to be revised after the study starts, the sponsor will determine how the revision impacts the study and how the revision should be implemented. The details of the revision will be documented and described in the clinical study report.

11 PROCEDURES AND INSTRUCTIONS (ADMINISTRATIVE PROCEDURES)

11.1 Changes to the Protocol

Any change to the protocol requires a written protocol amendment or administrative change that must be approved by the sponsor before implementation. Amendments specifically affecting the safety of subjects, the scope of the investigation, or the scientific quality of the study require submission to health or regulatory authorities as well as additional approval by the applicable IRBs/IECs. These requirements should in no way prevent any immediate action from being taken by the investigator, or by the sponsor, in the interest of preserving the safety of all subjects included in the study. If the investigator determines that an immediate change to or deviation from the protocol is necessary for safety reasons to eliminate an immediate hazard to the subjects, the sponsor's medical monitor and the IRB/IEC for the site must be notified immediately. The sponsor must notify the health or regulatory authority as required per local regulations.

Protocol amendments that affect only administrative aspects of the study may not require submission to health or regulatory authority or the IRB/IEC, but the health or regulatory authority and IRB/IEC should be kept informed of such changes as required by local regulations. In these cases, the sponsor may be required to send a letter to the IRB/IEC and the Competent Authorities detailing such changes.

11.2 Adherence to the Protocol

The investigator will conduct the study in strict accordance with the protocol (refer to ICH E6, Section 4.5).

11.3 Monitoring Procedures

The sponsor's/CRO's CRA will maintain contact with the investigator and designated staff by telephone, letter, or email between study visits. Monitoring visits to each site will be conducted by the assigned CRA as described in the monitoring plan. The investigator will allow the CRA to inspect the clinical, laboratory, and pharmacy facilities to assure compliance with GCP and local regulatory requirements. The CRFs and subject's corresponding original medical records (source documents) are to be fully available for review by the sponsor's representatives at regular intervals. These reviews verify adherence to study protocol and data accuracy in accordance with local regulations. All records at the site are subject to inspection by the local auditing agency and IRB/IEC review.

In accordance with ICH E6, Section 1.52, source documents include, but are not limited to the following:

- Clinic, office, or hospital charts
- Copies or transcribed health care provider notes which have been certified for accuracy after production
- Recorded data from automated instruments such as IxRS, x-rays, and other imaging reports, (eg, sonograms, computerized tomography scans, magnetic resonance images, radioactive images, ECGs, rhythm strips, EEGs, polysomnographs, pulmonary function tests) regardless of how these images are stored, including microfiche and photographic negatives
- Pain, quality of life, or medical history questionnaires completed by subjects
- Records of telephone contacts
- Diaries or evaluation checklists
- Drug distribution and accountability logs maintained in pharmacies or by research personnel
- Laboratory results and other laboratory test outputs (eg, urine pregnancy test result documentation and urine dip-sticks)
- Correspondence regarding a study subject's treatment between physicians or memoranda sent to the IRBs/IECs
- CRF components (eg, questionnaires) that are completed directly by subjects and serve as their own source

11.4 Recording of Data

A CRF is required and must be completed for each subject by qualified and authorized personnel. All data on the CRF must reflect the corresponding source document, except when a section of the CRF itself is used as source document. Any correction to entries made on the CRF must be documented in a valid audit trail where the correction is dated, the individual making the correction is identified, the reason for the change is stated, and the original data are not obscured. Only data required by the protocol for the purposes of the study should be collected.

The investigator must sign each CRF. The investigator will report the CRFs to the sponsor and retain a copy of the CRFs.

11.5 Identification of Source Data

All data to be recorded on the CRF must reflect the corresponding source documents.

11.6 Retention of Records

The circumstances of completion or termination of the study notwithstanding, the investigator is responsible for retaining all study documents, including but not limited to the protocol, copies of CRFs, the Investigator's Brochure, and regulatory agency registration documents (eg, Form FDA 1572 ICFs, and IRB/IEC correspondence). In addition, the sponsor will send a list of treatment codes by study subject to the investigator after the clinical database for this study has been locked. The site should plan to retain study documents, as directed by the sponsor, for at least 2 years after the last approval of a marketing application in an ICH region and until there are no pending or contemplated marketing applications in an ICH region or at least 3 years have elapsed since the formal discontinuation of clinical development of the investigational product.

It is requested that at the completion of the required retention period, or should the investigator retire or relocate, the investigator contact the sponsor, allowing the sponsor the option of permanently retaining the study records.

11.7 Auditing Procedures and Inspection

In addition to the routine monitoring procedures, the sponsor's Clinical Quality Assurance department conducts audits of clinical research activities in accordance with the sponsor's SOPs to evaluate compliance with the principles of ICH GCP and all applicable local regulations. If a government regulatory authority requests an inspection during the study or after its completion, the investigator must inform the sponsor immediately.

11.8 Handling of Study Drug

All study drugs will be supplied to the PI (or a designated pharmacist) by the sponsor. Drug supplies must be kept in an appropriate secure area (eg, locked cabinet) and stored according to the conditions specified on the drug labels. Investigational product will be stored in accordance with the DEA Regulations for Scheduled III - V Drugs and labeled storage conditions. The investigator (or a designated pharmacist) must maintain an accurate record of the shipment and dispensing of the study drug in a drug accountability ledger, a copy of which must be given to the sponsor at the end of the study. An accurate record of the date and amount of study drug dispensed to each subject must be available for inspection at any time. The CRA will visit the site and review these documents along with all other study conduct documents at appropriate intervals once study drug has been received by the site.

All drug supplies are to be used only for this study and not for any other purpose. The investigator (or site personnel) must not destroy any drug labels or any partly used or unused drug supply before approval to do so by the sponsor. At the conclusion of the study and as appropriate during the study, the investigator (or a designated pharmacist) will return all used and unused drug containers, drug labels, and a copy of the completed drug disposition form to the sponsor's CRA.

